6.2.3.2 Bleeding times

The bleeding times as measured by Simplate II[®] technique will be read directly from the CRF. Bleeding times which are recorded as being greater than 60 minutes will be treated as being exactly 60 minutes in calculating the mean, but all summary statistics associated with that observation will be asterisked and identified with a footnote indicating that the summary statistics are biased.

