1. INTRODUCTION

1.1 Background

Adenosine diphosphate (ADP) is an important mediator of platelet activation and aggregation through its binding to at least two distinct subtypes of purinoceptor, designated P2Y₁ and P2Y₁₂, found on platelets. Two ADP receptor antagonists, clopidogrel and ticlopidine have shown clear benefits for the reduction of clinical thromboembolic events in patients with atherosclerosis due to their ability to block the P2Y₁₂-receptor. However, since this blockade is irreversible and usually incomplete, the search continues for agents, which can further improve the clinical outcomes of these patients through improved efficacy or safety.

AZD6140 is a potent, selective P2Y₁₂-receptor antagonist (antiplatelet agent) being developed to reduce thromboembolic events in patients with atherosclerosis. It is orally active and does not require metabolic activation. Unlike clopidogrel and ticlopidine, which incompletely block the P2Y₁₂-receptor response in humans, pre-clinical studies indicate that AZD6140 can produce long-lasting and complete inhibition of ADP-induced platelet aggregation *ex vivo* following oral dosing.

Five phase I clinical trials conducted primarily in Caucasians have been completed. Two studies (SC-532-5169, SC-532-5171) have examined the tolerability of single oral doses ranging from 0.1 mg to 400 mg in healthy subjects. Complete inhibition of platelet aggregation was achieved with 100 to 400 mg doses. Mean bleeding times increased 3.0, 2.6, 2.5 and 7.4 fold 2 hours following doses of 100, 200, 300 and 400 mg respectively. The primary metabolite of AZD6140, AR-C124910XX, was present in significant (approximately 30% of parent) quantities. *In vitro* studies have shown this metabolite to be equipotent with the parent compound.

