6.4.2 Pharmacodynamics

Percentage of platelet aggregation inhibition will be summarized using descriptive statistics over time by dose and ethnic group. Mean (or median) percentage of platelet aggregation versus time by dose and ethnic group will be presented graphically. Differences (Japanese – Caucasian) in mean (or median) percentage of platelet aggregation inhibition will be summarized by dose.

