6.4.3.2 Bleeding times

Bleeding time and change from baseline in bleeding time will be summarized by time after dose, dose and ethnic group using descriptive statistics. Baseline will be defined as the pre-dose measurement taken at each visit. Differences in change from baseline (Japanese – Caucasians) will also be summarized by time and dose. Mean bleeding time versus time by dose and ethnic group will be displayed graphically. Individual bleeding times versus time will also be displayed graphically by dose and ethnic group.

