2. Since the bleeding time of many people is increased after the ingestion of aspirin,⁵ it is important to determine whether or not the patient has consumed drugs affecting platelet function, such as aspirin or aspirin-containing drugs, within a minimum of one week prior to testing.

EXPECTED RESULTS

Bleeding time studies with **Simplate** devices were conducted in several laboratories to estimate the variation present among normal subjects. These populations consisted of healthy, adult males and females, free from drugs or conditions known to affect the bleeding time. No significant lab-to-lab differences were observed for the various populations; thus, a composite population was formed that consisted of 187 males and females ranging from age 20 to 71 years. After log transformation, the expected range was calculated as a mean, plus or minus two standard deviations.

EXPECTED RANGE: 2.3 to 9.5 minutes

Because of the complexity of the primary hemostatic mechanism, the numerous patient-related factors that may affect the bleeding time (age, skin type, skin condition, vascularity, and temperature) and variation in individual techniques, it is recommended that each laboratory establish its own "expected range."

PERFORMANCE CHARACTERISTICS

The **Simplate** bleeding time procedure provides results that correlate with the Ivy and Mielke techniques. Correlation coefficients of 0.87 and 0.74 were obtained for Mielke and Ivy comparisons, respectively.

Precision

The precision between duplicate bleeding time determinations was studied in five laboratories. The standard deviation of duplication was not significantly different from one laboratory to the next ($p > 0.05$) and averaged 0.94 minutes (standard deviation of duplicates).

A study of the sources of variability with the **Simplate** device showed that approximately 40% of the total variability was attributed to day-to-day differences for the same subject; lesser variability was associated with the duplicate and subject-to-subject components. Similar variability was noted in a parallel study with the template procedure.

Clinical Pharmacology Study Protocol: Appendix D

Drug Substance	AZD6140
Study Code	D5130C05266
Edition No.	Final Version 1.0

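### Bleeding times over 60 minutes are averaged as exactly 60, so where such values occur the Japanese-Caucasian mean difference is biased, and no censoring-robust summary is named

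*Protocol*

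**What the plan says.** Protocol Section 6.2.3.2 fixes the rule: "Bleeding times which are recorded as being greater than 60 minutes will be treated as being exactly 60 minutes in calculating the mean". The same sentence adds that "all summary statistics associated with that observation will be asterisked and identified with a footnote indicating that the summary statistics are biased".

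Section 6.4.3.2 sets the analysis: "Bleeding time and change from baseline in bleeding time will be summarized by time after dose, dose and ethnic group using descriptive statistics". The ethnic comparison follows: "Differences in change from baseline (Japanese – Caucasians) will also be summarized by time and dose". The statistic behind that difference is not named. The group plot is explicit: "Mean bleeding time versus time by dose and ethnic group will be displayed graphically". Individual bleeding times are also to be plotted by dose and ethnic group.

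For platelet aggregation, Section 6.4.2 leaves a choice: "Differences (Japanese – Caucasian) in mean (or median) percentage of platelet aggregation inhibition will be summarized by dose". The bleeding-time section has no such wording.

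Bleeding time is one of the two pharmacodynamic measures in the secondary objective that compares the ethnic groups (Section 2.1). Section 4.3.2 expects that some values may still exceed 60 minutes at 24 h, since it plans a repeat test for them.

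**The concern.** A value recorded as more than 60 minutes is right-censored: all that is known is that it exceeds 60. Entering it as 60 lowers the mean of whichever group has more such values. If Japanese subjects bled longer than Caucasian subjects with a similar log-scale spread, their mean would be pulled down further and the difference would look smaller than it is. In the first study of the drug in Japanese subjects, that is an unfavourable direction for an error.

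The protocol recognizes the bias, but an asterisk gives neither its direction nor its size, and no alternative estimate is named. The protocol therefore states the estimator and admits that it is biased, which is more than a detail left open for the statistical analysis plan.

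**Working it through.** The protocol gives no design figure for bleeding time (Section 6.5 covers only AUC and Cmax), so there is none to reproduce. The check asks how far the cap moves a mean difference when the protocol's own bleeding-time figures are used.

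**Inputs from the protocol**
- Appendix C: expected range 2.3 to 9.5 min, obtained thus: "After log transformation, the expected range was calculated as a mean, plus or minus two standard deviations".
- Section 1.1: "Mean bleeding times increased 3.0, 2.6, 2.5 and 7.4 fold 2 hours following doses of 100, 200, 300 and 400 mg respectively".
- Section 6.5: 8 active subjects per ethnic group and cohort, to achieve 6 evaluable.

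**Assumptions, not in the protocol**
- Post-dose times are lognormal with the same log-SD *s* in both groups, from 0.355 (the Appendix C value) to 0.8.
- The true Japanese/Caucasian ratio of means is 1.25, 1.5 or 2.
- The Section 1.1 fold rises apply to the Caucasian mean.

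**Baseline**
- Geometric mean = exp[(ln 2.3 + ln 9.5)/2] = 4.67 min
- Log-SD = (ln 9.5 − ln 2.3)/4 = 0.355
- Arithmetic mean = 4.67 × exp(0.355²/2) = 4.98 min

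Section 1.1 reports rises in the mean, so they are applied to 4.98. This gives Caucasian means of 14.9, 12.9, 12.4 and 36.8 min at 100, 200, 300 and 400 mg.

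**Capped mean**

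For true mean *m*: μ = ln *m* − *s*²/2 and *a* = (ln 60 − μ)/*s*. Then E[min(X, 60)] = *m*·Φ(*a* − *s*) + 60·[1 − Φ(*a*)].

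Pre-dose values lie far below 60, because Section 4.3.2 does not allow dosing above 9 min. The bias in a difference of mean changes therefore equals the bias in the difference of post-dose means.

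**Worked case: 400 mg, s = 0.355, ratio 1.5**
- Caucasian: *m* = 36.8, μ = 3.544, *a* = 1.55, share over 60 = 6%, capped mean 36.2.
- Japanese: *m* = 55.3, μ = 3.949, *a* = 0.41, share over 60 = 34%, capped mean 49.3.
- True difference 18.4 min; capped difference 13.1 min; 29% lost.

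**Range at 400 mg**

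| Ratio | True difference (min) | Capped, s = 0.355 | Capped, s = 0.5 | Capped, s = 0.7 | Capped, s = 0.8 | Share lost |
|---|---|---|---|---|---|---|
| 1.25 | 9.2 | 7.4 | 6.3 | 5.3 | 4.8 | 20-47% |
| 1.5 | 18.4 | 13.1 | 11.3 | 9.5 | 8.8 | 29-52% |
| 2 | 36.8 | 19.7 | 17.7 | 15.5 | 14.6 | 46-60% |

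**100 to 300 mg.** The loss is 0-5% for *s* up to 0.5, 4-15% at 0.7, and up to about 20% at 0.8.

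**Direction.** In simulated samples of 8 against 8 at 400 mg with ratio 1.5 and *s* from 0.35 to 0.70, the cap shrank the observed difference in 84-92% of runs and enlarged it in 6-14%. The sign is less secure with unequal spread. With equal true means of 36.8 min but log-SD 0.35 (Caucasian) and 0.90 (Japanese), the capped Japanese mean comes out 6.8 min lower. With a true ratio of 1.1, a difference of +3.7 min becomes −4.9 min.

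**Medians.** At 400 mg and *s* = 0.355 the Caucasian median is 34.6 min. The Japanese median is 43.2 min at ratio 1.25 and 51.9 min at 1.5, so the cap leaves the median difference (8.6 and 17.3 min) unchanged. At ratio 2 the Japanese median is 69.2 min. It would have to be printed as >60, and the median difference is then known only to exceed 60 − 34.6 = 25.4 min.

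**The case against.** Several points on the other side stand.

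- The bias is disclosed for every affected statistic, and the individual plots would show values sitting at the cap. This limits the harm but does not replace the group estimate.
- Section 6.4.3.2 does not name the statistic for the ethnic difference, and its descriptive statistics may well include medians and counts once the statistical analysis plan is written. Their absence from the protocol is not the finding. The finding is that the protocol does name the capped mean and does plot it.

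A reader might also infer more than the documents support.

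- *That censoring at 400 and 600 mg will be common.* The 7.4-fold rise is from 2 h, whereas this study measures at 4.5 and 24 h. No bleeding-time figure is given for 600 mg. The 300 mg rise (2.5-fold) is the lowest of the four, so the case for high doses rests on 400 mg alone.
- *That the true difference is always shrunk.* That is the likely result under similar log-scale spread, but not under unequal spread.
- *That Appendix C requires a log-scale analysis.* It describes how a reference range was derived in 187 healthy adults and sets no analysis scale for this trial.
- *That bleeding time is the trial's main comparison.* The primary objective does not list it, and Section 6.2 names only platelet aggregation inhibition as the pharmacodynamic comparison. It belongs to a secondary objective and is summarized descriptively.

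**Conclusion.** The point holds where values over 60 minutes occur. There the capped mean difference is biased, most likely towards no ethnic difference if one group is shifted longer with similar log-scale spread. The footnote reports this without correcting it.

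On the protocol's own figures the effect could be material at 400 mg, at 20-60% of a true mean difference for ratios 1.25 to 2. It is slight at 100 to 300 mg unless the spread is large. These sizes depend on lognormal times, the assumed spread and ratios, and the 2 h rise carrying over to this study's measurement times. They illustrate the mechanism and do not forecast the result; the amount of censoring at 4.5 h, at 24 h and at 600 mg is unknown.

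The rule should be changed because a robust summary is available at almost no cost. It does not bear on the primary objective.

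**What to change.** Amend Sections 6.2.3.2 and 6.4.3.2 as follows.

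- Base the bleeding-time summaries, the group plot and the Japanese-Caucasian comparison on medians and quartiles. Print them as >60 when they fall in the censored range, and give a change or difference that depends on such a value as a bound.
- Report the number of subjects over 60 minutes for each dose, time and ethnic group.
- Keep the capped mean, if at all, only as a supplement with its existing flag.
- Optionally add a censored-lognormal Japanese/Caucasian ratio with a 90% confidence interval, the level already used for pharmacokinetics in Section 6.1, as supportive analysis only. With 6 to 8 subjects per group it relies heavily on the assumed upper tail.

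The cost is a wording change and some programming, with no new data or procedures. The limitation is that when more than half of a group exceeds 60 minutes, its median is known only to be above 60, so the counts must be read beside it.

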6.2.4 Safety

The incidence, nature and severity of adverse events will be obtained from the CRF data. All variables relating to laboratory measurements, 12-lead ECG and vital signs, as detailed in Section 4.4, will be included in the analysis. Changes from baseline for each dose level will be relative to the latest pre-dose value on Day -2/-1 at Visits 2, 3 and 4, respectively.

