No serious adverse events (SAE) were observed in the 5 trials completed to date, which exposed healthy subjects to daily doses from 0.1 mg to 600 mg for periods of up to 20 days. Approximately 120 healthy subjects were entered into these trials, and 89 healthy subjects received at least 1 dose of AZD6140. Petechiae, tachycardia, and postural hypotension were the most common adverse events reported in some of these trials. However, the causal relationship of these adverse events to AZD6140 is uncertain. Four subjects in Study SC-532-5256 (single 200 mg dose study in healthy subjects) reported rashes that were considered by the investigator to have a reasonable possibility of a causal relationship to study treatment. Two of these subjects were withdrawn because of this adverse event.

In the multiple ascending dose study SC-532-5239, 1 subject had an increase in liver transaminases of more than 3 times the upper limit of normal after 4 daily doses of 300 mg AZD6140, and was discontinued from the study. The transaminases returned to normal over 24 days. Another subject had a milder increase in transaminase after 4 twice-daily doses of 200 mg that improved despite continuation and increase in dose of AZD6140. There were no other laboratory findings, and no ECG, Holter monitor or vital signs findings of concern during any of the studies.

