3.1.5 Washout Periods

At the completion of the assessments and procedures for Day 4 of **Visits 2 and 3**, the subjects will be discharged from the CRC and enter a washout period of at least 5 days from study drug dosing. Subjects will return to the CRC on the evening prior to receiving the next dose of study drug (Day -1).

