Two ECGs approximately 1 minute apart will be performed at each of the following time points:
Visit 2: Day –1 at 1, 2, 3, 4, 8, 12 and 24 hours post theoretical dose.
Visits 2, 3 and 4: Day 1 at 1, 2, 3, 4, 8, 12 and 24 hours post dose.
- b **Sitting blood pressure and pulse (after sitting for 5 minutes) will be taken at the following times:**
Visit 1 (Screening)
Visits 2: Day –2, Visits 2, 3 and 4: Days –1, 1, 2, 3 and 4
Visit 5 (Follow-up)
Orthostatic blood pressure assessments (after 10 minutes supine and after 2 minutes standing) will be performed at the following times:
Visits 2, 3 and 4: 4 hours post dose
- c Blood samples for clinical chemistry, hematology and urinalysis will be obtained at the following times:
Visit 1 (Screening)
Visit 2: Day –2 and at 24 hours post dose
Visits 3 and 4: Day –1 and at 24 hours post dose
Visit 5 (Follow-up)
- d Blood samples for ALT, AST, GGT, alkaline phosphatase and total bilirubin will be obtained at the following times:
Visits 2, 3 and 4: predose
- e Randomization will occur at Visit 2 only.
- f Blood samples for pharmacokinetics will be collected at the following time points:
Visits 2, 3 and 4: Pre-dose, 0.5, 1, 2, 3, 4, 6, 8, 12, 18, 24, 36, 48, and 72 hours post dose.
- g Blood samples for platelet aggregometry will be collected at the following time points:
Visits 2, 3 and 4: pre-dose, 2, 4, 12, and 24 hours post dose.
- h Bleeding time will be assessed at the following time points:
Visit 1 (Screening)
Visits 2, 3 and 4: pre-dose, 4.5 and 24 hours post dose.
- i A single blood sample for genetic analysis will be obtained prior to dosing at Visit 2 only.
- j Visits 3 and 4 only
- k Serum pregnancy tests will be performed at Visit 1 (Screening) and Visit 5 (Follow-up).
Urine pregnancy tests will be performed at Visit 2, Day –2 and at Visits 3 and 4, Day –1.

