4.6 Volume of blood sampling

The total volume of blood that will be drawn from each subject in this study is as follows:

Table 5 Volume of blood to be drawn from each subject

Assessment	Sample volume (mL)	No. of samples	Total volume (mL)
PK samples	2	42	84
Genetic sample	9	1	9
ADP induced platelet aggregation	4.5	30	135
HIV, HBsAg, hepatitis C	10	1	10
Clinical chemistry	10	8	80
Hematology	9.5	8	76
Limited chemistry panel	10	3	30
Serum pregnancy test	1	2	2
Total			426

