3.1.4 Visit 4 (Days –1, 1, 2, 3 and 4)

Previous Text:

The following sentence is moved to the beginning of Section 3.1.2 for clarity:

Note: Throughout the study the site will supply standardized meals while the subjects remain at the CRC. Menus will be approved by the sponsor.

Section of protocol affected:

Table 1 Study Plan

Previous Text:

Table 1 is updated to reflect the following changes:

The screening period is extended from 21 days to 28 days in order to allow more time for recruitment of subjects at the site.

The Brief Physical Exam scheduled for Visit 2, Day -2 is changed to a Physical Exam scheduled for Visit 2, Day -2 in order to establish a baseline evaluation.

The Limited Chemistry Panel scheduled for Visits 2, 3 and 4, Day -1 is changed to Visits 2, 3 and 4, Day 1 predose.

Randomization of study medication scheduled for Visit 2, Day -2 is changed to Visit 2, Day 1.

Section of protocol affected:

Table 1 Study Plan

Previous Text:

Footnote b:

Sitting blood pressure and pulse (after sitting for 5 minutes) will be taken at the following times:

Visit 1 (Screening)

Visits 2: Day -2, Visits 2, 3 and 4: Days -1, 1, 2, 3 and 4

Visit 5 (Follow-up)

Orthostatic blood pressure assessments will be performed at the following times:

Visits 2, 3 and 4: 4 hours post dose

Revised Text:

Footnote b:

Sitting blood pressure and pulse (after sitting for 5 minutes) will be taken at the following times:

Visit 1 (Screening)

Visits 2: Day -2, Visits 2, 3 and 4: Days -1, 1, 2, 3 and 4

Visit 5 (Follow-up)

Orthostatic blood pressure assessments (after 10 minutes supine and after 2 minutes standing) will be performed at the following times:

Visits 2, 3 and 4: 4 hours post dose

Reason for Amendment:

The positions for orthostatic blood pressure assessments were added for clarity.

Section of protocol affected:

Section 3.3.3 Exclusion Criteria

Previous Text:

2. Current and/or past history of intolerance or hypersensitivity to drugs with a similar chemical structure or mechanism of action of AZD6140 or any ingredient in its formulation (refer to section 2.4.1). These drugs include, but are not limited to clopidogrel (Plavix) and ticlopidine (Ticlid).

Revised Text:

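### With each visit's own pre-dose value as the only stated reference, laboratory change scores cannot attribute a rise that starts more than 24 h after dose 1 or 2.

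*Protocol*

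**What the plan says.** Protocol section 6.2.4 fixes the reference for safety changes: "Changes from baseline for each dose level will be relative to the latest pre-dose value on Day -2/-1 at Visits 2, 3 and 4, respectively". The protocol states no second reference for laboratory variables.

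Table 1, footnote c, sets the chemistry, hematology and urinalysis times. For the first dosing visit they are "Visit 2: Day –2 and at 24 hours post dose"; for the other two, "Visits 3 and 4: Day –1 and at 24 hours post dose". Screening and Visit 5 add one sample each. Footnote d adds a liver panel ("Blood samples for ALT, AST, GGT, alkaline phosphatase and total bilirubin will be obtained at the following times"), which is drawn predose at Visits 2, 3 and 4. Amendment 1 records its present position: "The Limited Chemistry Panel scheduled for Visits 2, 3 and 4, Day -1 is changed to Visits 2, 3 and 4, Day 1 predose".

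Section 3.1.5 has subjects "enter a washout period of at least 5 days from study drug dosing". Section 3.1 gives 8 of the 10 subjects in each cohort of each ethnic group active drug on all three occasions. Section 3.1.6 puts Visit 5 at 7 to 14 days after the last dose.

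Section 1.1 describes one subject in the multiple-dose study whose transaminases passed 3 times the upper limit of normal after 4 daily doses of 300 mg. Of that case it says: "The transaminases returned to normal over 24 days".

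**The concern.** For subjects on active drug, the Visit 3 baseline follows one active dose and the Visit 4 baseline follows two. The interval suits the plasma half-life of 6 to 13 hours given in section 1.1. A liver enzyme can lag behind exposure and recover slowly, and the one marked case the protocol reports took far longer than five days to resolve.

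If a rise begins after the 24 h sample that follows dose 1 or 2, it is first measured at the next visit, before the next dose. Under section 6.2.4 that value is a baseline. The causing dose then shows no change, and the next dose is measured from a raised starting point.

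Laboratory parameters are part of the primary objective, and the transaminase rises are the laboratory findings that section 1.1 reports from earlier trials. The change summaries by dose and ethnic group are where a reader would look for a liver signal that differs by dose or between Japanese and Caucasian subjects.

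**Working it through.** **Schedule.** Chemistry samples from footnote c: screening 1 + Visit 2 (Day −2, 24 h) 2 + Visit 3 (Day −1, 24 h) 2 + Visit 4 (Day −1, 24 h) 2 + follow-up 1 = 8. Table 5 agrees ("Clinical chemistry 10 8 80": volume, number, total). The liver panel adds 3 samples, all predose.

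**Post-dose liver values belonging to each dose.**
- Dose 1 (50 or 100 mg): 24 h only.
- Dose 2 (200 or 300 mg): 24 h only.
- Dose 3 (400 or 600 mg): 24 h and Visit 5.

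With the minimum five-day interval, the next Day −1 is the fourth day after the previous dose. Arrival is in the evening, so the sample falls about 4 to 4.5 days after it.

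**Assumed illustration.** None of these ALT values comes from the protocol. One subject has ALT 25 U/L before dose 1, no rise up to 24 h, a linear rise to a peak P on day 4, then a linear return over 24 days. Later doses have no effect. With d in days from dose 1:
- d ≤ 1: ALT = 25
- 1 < d ≤ 4: ALT = 25 + (P − 25)(d − 1)/3
- d > 4: ALT = P − (P − 25)(d − 4)/24, not below 25

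Take P = 75 and doses on days 0, 5 and 10.
- Baselines: Visit 2, 25. Visit 3 (day 4), 75. Visit 4 (day 9), 75 − 50 × 5/24 = 64.6.
- 24 h values: day 1, 25. Day 6, 75 − 50 × 2/24 = 70.8. Day 11, 75 − 50 × 7/24 = 60.4.
- Changes under section 6.2.4: 25 − 25 = 0; 70.8 − 75 = −4.2; 60.4 − 64.6 = −4.2.
- Changes from the Visit 2 value: 0; 70.8 − 25 = +45.8; 60.4 − 25 = +35.4.

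Placing the Visit 3 baseline at day 4.5 makes it 75 − 50 × 0.5/24 = 74.0 and the dose 2 change about −3.1. The picture is the same.

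**Range.** For P from 50 to 120 and dose spacing of 5 to 14 days, the per-visit 24 h changes after doses 2 and 3 run from −1.0 to −7.9 and are never positive. Against the Visit 2 value, the dose 2 change runs from +13.5 to +87.1.

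**Effect on a group mean.** If this is one of 8 active subjects and the others do not change, the mean change at dose 2 is −4.2/8 = −0.5 under the plan and 45.8/8 = +5.7 from the Visit 2 value.

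**Rise still climbing at the next baseline.** Move the peak to day 6. ALT on day 4 is 25 + 50 × 3/5 = 55 and on day 6 is 75. Dose 2 is then credited with 75 − 55 = +20 of an excess of 50 that dose 1 caused. Here the attribution is to the wrong dose.

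**Same rise after dose 3 (P = 75).** The change is 0 at 24 h. At Visit 5 it is 68.8 − 25 = +43.8 on day 7 and 54.2 − 25 = +29.2 on day 14, against the Visit 4 baseline. The late effect of the last dose is captured.

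**The case against.** A per-visit baseline is a common and legitimate choice for dose-specific change in an ascending-dose design. A Visit 2 reference would accumulate the effects of earlier doses in later changes and blur attribution the other way. That stands, and it is why the Visit 2 change should supplement the per-visit change and not replace it.

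A reader might infer that a raised enzyme would be hidden. The protocol does not support that. Section 6.4.3.3 lists and summarizes the laboratory values themselves by dose, ethnic group and measurement time, and flags values out of range. Section 3.1.7 has safety laboratory results reviewed before each escalation, and section 4.4.2 rechecks eligibility on Day −1 of Visits 3 and 4. What remains is narrower: nothing in these provisions assigns a Visit 3 or 4 pre-dose value to the dose that came before it, so the summaries by dose still lack it as a late value.

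A reader might also infer that a late rise is credited to no dose at all. That fails for 400 and 600 mg, where Visit 5 follows, and for a rise still climbing at the next baseline.

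A third tempting step is to treat the 24-day recovery as proof of carry-over. Both transaminase cases in section 1.1 came from repeated dosing, and the milder one improved despite continued and increased dosing. That section reports no other laboratory findings in those studies, which included single doses up to 400 mg. Nor can the 24 days be scaled to the five-day interval to show what is missed. If recovery began at dosing, 1 − 1/24 = 96% of the excess would be present at 24 h and credited to the right dose.

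Finally, section 6.7 leaves data presentation to the SAP. That covers layout, but the baseline rule is fixed in the protocol itself.

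**Conclusion.** The point holds for change-from-baseline laboratory summaries. For 50, 100, 200 and 300 mg, a rise starting after 24 h gives a change of about zero for its own dose. The next dose (200, 300, 400 or 600 mg) then shows about zero or a fall, or part of the rise if it is still climbing. In the illustration the sign of the dose 2 result turns on the reference alone: −4.2 against +45.8.

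This rests on late onset after a single dose, which the protocol does not document, and on assumed ALT values and linear recovery. It concerns active subjects only; placebo subjects have no earlier exposure to carry forward. It does not show that subjects are unprotected or that raised values go unreported, and no hypothesis test depends on the change score. It is an inexpensive improvement to a summary that serves the primary objective.

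**What to change.** In section 6.2.4, keep the per-visit change and add for laboratory variables:
- change from the last value before the first dose (Visit 2);
- the pre-dose values of Visits 3 and 4 presented also as late post-dose observations of the preceding dose, with Visit 5 as the late observation for dose 3, by dose and ethnic group.

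The same edit should reconcile the Day −2/−1 wording with Table 1, where the latest predose liver panel is now on Day 1, and state which value serves as baseline.

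The cost is wording and one more set of summaries from samples already scheduled. Late values will fall on variable days after dosing because five days is a minimum, so the actual day should be shown. The Visit 2 change needs a note that it accumulates the effects of earlier doses.
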